4.3.3 Clinical Laboratory, Blood Sample and Urinalysis

4.3.3.1 Definitions and Derivations

Hematology, serum clinical chemistry, coagulation, cardiac biomarker, and urinalysis will be performed as per the schedule of events (refer to Protocol Sections 1.3 and 8.2.4 for

schedule and lists of parameters). A urine pregnancy test will be performed at screening and per the schedule of events (refer to Protocol, Section 1.3). If urine tests positive or indeterminate, a serum test will be performed for confirmation.

Quantitative laboratory parameters reported as “< X”, i.e. below the lower limit of quantification (BLQ) or “> X”, i.e. above the ULOQ, will be converted to X for the purpose of quantitative summaries, but will be presented as recorded, i.e. as “< X” or “> X” in the listings.

Quantitative laboratory parameters will be compared with the relevant central laboratory normal ranges in SI units and categorized as:

- Low: Below the lower limit of the laboratory normal range.
- Normal: Within the laboratory normal range (upper and lower limit included).
- High: Above the upper limit of the laboratory normal range.

Quantitative laboratory parameters with available Common Terminology Criteria for Adverse Events (CTCAE) toxicity grades will be categorized as follows where higher grades representing a more severe toxicity (refer to Appendix [A 2](#)) for each parameter toxicity grade criteria):

- Grade 1 (i.e., mild);
- Grade 2 (i.e., moderate);
- Grade 3 (i.e., severe);
- Grade 4 (i.e., life-threatening);
- Grade 5 (i.e., death).

Although not defined in the CTCAE toxicity grading system, version 5, non-missing laboratory parameter results not meeting any of the 5 grades defined in the CTCAE toxicity grading system will be categorized as ‘No Event’ for the purpose of the shift from baseline summaries.

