4.3.3.2 Presentations

The following summaries will be provided by actual treatment group for laboratory parameters:

- Observed and change from baseline in Standard International (SI) units by visit (for quantitative parameters).
- Observed and change from baseline for Illness Visits as defined in Section [3.3.1](#) (for coagulation parameters) in SI units by Illness Visit (the Illness Visits where the

series corresponds to positive RT-PCR test, as defined in Section 4.2.3.4.1, will be used in the summary).

- Number and percentage of participants in each laboratory parameter category by visit (for categorical parameters).
- Maximum post-baseline ALT/AST observed value categorized as $< 3 \times$ upper limit of normal (ULN), ≥ 3 to $< 5 \times$ ULN, ≥ 5 to $< 10 \times$ ULN or ≥ 10 ULN by maximum post-baseline total bilirubin (TBL) observed value categorized as $< 2 \times$ ULN or $\geq 2 \times$ ULN.
- Heatmap of the maximum post-baseline observed value in ALT value by the maximum post-baseline observed value in TBL value, both expressed as multiple of ULN.
- Heatmap of the maximum post-baseline observed value in AST value by the maximum post-baseline observed value in TBL value, both expressed as multiple of ULN.
- A listing of participants with at least one observed value in ALT value $\geq 3 \times$ ULN, AST value $\geq 3 \times$ ULN or TBL value $\geq 2 \times$ ULN will be provided.
- Listing of participants with at least one abnormal laboratory observed value outside the normal range criteria (refer to Section 4.3.3.1).

The following further summaries may be provided by actual treatment group for laboratory parameters:

- Shift from baseline to the worst post-baseline observed value according to the CTCAE toxicity grades (for quantitative parameters with available CTCAE toxicity grades; refer to Section 4.3.3.1).
- Shift from baseline to the maximum/minimum post-baseline observed value according to normal range criteria (for quantitative parameters without available CTCAE toxicity grades; refer to Section 4.3.3.1).

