Blood bilirubin increased ¹	Total bilirubin (µmol/L)	>ULN - 1.5 x ULN if baseline was normal; > 1.0 - 1.5 x baseline if baseline was abnormal	>1.5 - 3.0 x ULN if baseline was normal; >1.5 - 3.0 x baseline if baseline was abnormal	>3.0 - 10.0 x ULN if baseline was normal; >3.0 - 10.0 x baseline if baseline was abnormal	>10.0 x ULN if baseline was normal; >10.0 x baseline if baseline was abnormal
Cholesterol high	Cholesterol (mmol/L)	>ULN - 7.75	>7.75 - 10.34	>10.34 - 12.92	>12.92
Creatine phosphokinase (CPK) increased	Creatine kinase (U/L)	>ULN - 2.5 x ULN	>2.5 x ULN - 5 x ULN	>5 x ULN - 10 x ULN	>10 x ULN
Creatinine increased ²	Creatinine	>ULN - 1.5 x ULN	>1.5 - 3.0 x baseline; >1.5 - 3.0 x ULN	>3.0 x baseline; >3.0 - 6.0 x ULN	>6.0 x ULN

CTCAE Term	Laboratory test	Grade 1	Grade 2	Grade 3	Grade 4
Gamma glutamyl transferase (GGT) increased ¹	GGT (U/L)	>ULN - 2.5 x ULN if baseline was normal; 2.0 - 2.5 x baseline if baseline was abnormal	>2.5 - 5.0 x ULN if baseline was normal; >2.5 - 5.0 x baseline if baseline was abnormal	>5.0 - 20.0 x ULN if baseline was normal; >5.0 - 20.0 x baseline if baseline was abnormal	>20.0 x ULN if baseline was normal; >20.0 x baseline if baseline was abnormal
Hemoglobin increased	Hemoglobin (g/dL)	Increase from ULN in >0 - 2	Increase from ULN in >2 - 4	Increase from ULN in >4	-
International normalized ratio (INR) increased ³	INR	>1.2 – 1.5	>1.5 – 2.5	>2.5	-
Lymphocyte count decreased	Absolute lymphocytes count (x 10E9/L)	<LLN – 0.8	<0.8 – 0.5	<0.5 – 0.2	<0.2
Lymphocyte count increased	Absolute lymphocytes count (x 10E9/L)	-	>4 – 20	>20	-
Neutrophil count decreased	Absolute neutrophils count (x 10E9/L)	<LLN – 1.5	<1.5 – 1.0	<1.0 – 0.5	<0.5

CTCAE Term	Laboratory test	Grade 1	Grade 2	Grade 3	Grade 4
Platelet count decreased	Platelet count (x10E9/L)	<LLN – 75.0	<75.0 – 50.0	<50.0 – 25.0	<25.0
White blood cell (WBC) decreased	WBC (x 10E9/L)	<LLN – 3.0	<3.0 – 2.0	<2.0 – 1.0	<1.0
Hypercalcemia ⁴	Corrected serum calcium (mmol/L)	>ULN – 2.9	>2.9 – 3.1	>3.1 – 3.4	>3.4
Hyperkalemia	Potassium (mmol/L)	>ULN – 5.5	>5.5 – 6.0	>6.0 – 7.0	>7.0
Hypernatremia	Sodium (mmol/L)	>ULN - 150	>150 - 155	>155 - 160	>160
Hypoalbuminemia	Albumin (g/dL)	<LLN - 3	<3 - 2	<2	-
Hypocalcemia ⁴	Corrected serum calcium (mmol/L)	<LLN - 2.0	<2.0 – 1.75	<1.75 – 1.5	<1.5

CTCAE Term	Laboratory test	Grade 1	Grade 2	Grade 3	Grade 4
Hypoglycemia	Glucose (mg/dL)	<LLN - 55	<55 - 40	<40 - 30	<30
Hypokalemia	Potassium (mmol/L)	-	<LLN - 3.0	<3.0 - 2.5	<2.5

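### In the optional CTCAE shift tables, high platelets, neutrophils and glucose, and WBC between ULN and 100 x 10E9/L, fall into 'No Event', and no planned laboratory table clearly counts them by arm

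*SAP*

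**What the plan says.** Appendix A 2 of the SAP lists the CTCAE terms used to grade laboratory results. Platelets, neutrophils and glucose have one row each: "Platelet count decreased", "Neutrophil count decreased" and "Hypoglycemia". All three are graded only below the lower limit of normal. White cells have a low-side row and a leukocytosis row, but the latter has a single entry, above 100 x 10E9/L. Other tests are graded on both sides; lymphocytes, for example, also have "Lymphocyte count increased".

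SAP 4.3.3.1 assigns "non-missing laboratory parameter results not meeting any of the 5 grades defined in the CTCAE toxicity grading system" to a category called 'No Event', for use in the shift tables. The same section derives Low, Normal and High for every quantitative parameter.

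SAP 4.3.3.2 then describes two shift tables. One is "Shift from baseline to the worst post-baseline observed value according to the CTCAE toxicity grades", for parameters that have grades. The other is the shift to the maximum/minimum value by normal range, given only "for quantitative parameters without available CTCAE toxicity grades". Both are introduced as summaries that may be provided, not as summaries that will be.

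**The concern.** Each rule is reasonable alone, but together they leave a hole. A test with a row in only one direction counts as a graded parameter, so it loses the normal-range shift in both directions. Its out-of-range values on the ungraded side then share a category with normal values.

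The outcome is uneven. Protocol 8.2.4 also measures tests with no A 2 row, such as MCV and urea; these are eligible for a shift table in both directions, while platelets and glucose are not. The SAP gives no reason for the difference.

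Safety is a primary objective. The protocol enrols participants on high-dose corticosteroids and with hematologic malignancies, so high glucose, neutrophil and white-cell values are plausible. Protocol 8.3.6 also limits AE reporting of mandated laboratory tests on the ground that their results will be summarized in the CSR, which places weight on the laboratory tables.

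**Working it through.** The plan states no figure to reproduce. The check applies the rules as written.

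**Step 1: direction of each A 2 row.** There are 30 rows covering 24 tests.
- Graded both ways, 6 tests: hemoglobin, lymphocytes, WBC, calcium, potassium, sodium.
- Low side only, 5 tests: platelets, neutrophils, glucose, albumin, eGFR.
- High side only, 13 tests: eosinophils, troponin I, aPTT, ALT, ALP, AST, bilirubin, cholesterol, creatine kinase, creatinine, GGT, INR, urine protein.
- Check: 6 x 2 + 5 + 13 = 30 rows; 6 + 5 + 13 = 24 tests.

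**Step 2: apply the cut-offs and the 'No Event' rule.** A 2 gives the boundaries for grades 2, 3 and 4. The lower limits of normal (150, 2.0 and 70) are assumed for illustration; the results for high values do not depend on them.

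| Test | Boundaries (grades 2, 3, 4) | Low values: grade | Normal value | High values |
|---|---|---|---|---|
| Platelets, x 10E9/L | 75, 50, 25 | 100: 1; 60: 2; 40: 3; 20: 4 | 250: No Event | 500, 1000, 1500: No Event |
| Neutrophils, x 10E9/L | 1.5, 1.0, 0.5 | 1.8: 1; 1.2: 2; 0.7: 3; 0.3: 4 | 5: No Event | 10, 20, 50: No Event |
| Glucose, mg/dL | 55, 40, 30 | 60: 1; 45: 2; 35: 3; 25: 4 | 90: No Event | 200, 400, 800: No Event |

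For WBC, a value of 90 x 10E9/L is not low and does not exceed 100, so it is also 'No Event'.

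**Step 3: look for another planned count of high values.**
- Normal-range shift (4.3.3.2): excluded, because these parameters have grades.
- Category counts by visit (4.3.3.2): specified for categorical parameters. The text does not say that this includes the Low/Normal/High category of a quantitative test.
- Observed value and change by visit (4.3.3.2): planned, by arm. SAP 3.3 says continuous variables may be summarized with quartiles, minimum and maximum as well as the mean. This shows the distribution, not the number of participants who became high.
- Out-of-range output (4.3.3.2): a participant listing, not a table.
- AE tables (SAP 4.3.2.2): count a high value only if it was reported as an AE under protocol 8.3.6, that is, if it met an SAE criterion, led to discontinuation of IMP, or was judged clinically relevant.

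**Step 4: size.** The documents give no rate of high values. If a proportion p of the 100 planned participants in an arm had at least one high glucose, 100 x p participants would lack a planned laboratory count. Assumed values of 10%, 20% and 30% give 10, 20 and 30 per arm, less any reported as AEs.

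**The case against.** The strongest reply is that this is a presentation gap in optional descriptive tables. Most of that reply stands.

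- Both shift tables are optional, and the label applies only to shift summaries. It would be wrong to infer that every high value will be tabulated as 'No Event'; that happens only if the CTCAE shift table is produced.
- High values are not lost. They enter the by-arm, by-visit summaries and the listing, and clinically relevant ones are counted as AEs by arm. A reader might infer that the outputs cannot show a difference between the regimens. The documents do not support that: a maximum would show an extreme value, and a common rise would tend to move the upper quartile.
- A reader might also infer that a thrombotic signal would be hidden. It would not rest on platelet counts. D-dimer, P-selectin, thrombin and Factor VIII are measured and have no A 2 row, so they qualify for the normal-range shift. Thromboembolic events are AESIs, cardiovascular events are adjudicated, and embolic and thrombotic SAEs have their own tables.
- 'No Event' is literally correct against a term that names a decrease.

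These points limit the consequence but do not supply the missing count. If the shift tables are produced, they merge high with normal for these tests. If they are omitted, no other planned laboratory table clearly counts participants with a high value. A sponsor could say the normal-range shift is meant to apply to whichever direction is ungraded, but the text excludes parameters, not directions.

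**Conclusion.** The point holds in a limited form. In the optional CTCAE shift tables, all above-ULN platelet, neutrophil and glucose results, and WBC from ULN to 100 x 10E9/L, would be classed as 'No Event'. The normal-range shift that would show them is closed to graded parameters. Because the shift uses each participant's worst value, someone with both a graded low and a high result appears under the low grade, and the high result is still not counted. The same gap affects the ungraded side of the other one-direction tests.

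No hypothesis is tested and the underlying data are reported elsewhere, so this is a cheap improvement to the safety tables, not a threat to the safety conclusions. It rests on two readings: that a parameter with any A 2 row counts as having CTCAE grades, and that the by-visit category counts do not cover Low/Normal/High for quantitative tests. If the sponsor intends otherwise on either, saying so in the SAP would remove much of the gap.

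**What to change.** In SAP 4.3.3.2, provide the normal-range maximum/minimum shift for all quantitative parameters, and move it to the list of summaries that will be provided. Extending the bullet while leaving it optional would not guarantee the count. The minimum alternative is to provide that shift for any direction not graded in A 2, plus high WBC, which must be named because its high side is nominally graded.

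In SAP 4.3.3.1, label such results 'Outside normal range, not graded' and keep 'No Event' for the rest. If the label is applied to every test, it will also catch some results on a graded side, such as an ALT above ULN that does not reach the grade 1 multiple of an abnormal baseline. A footnote can explain this.

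The cost is two SAP edits and a few extra descriptive tables. The Low/Normal/High category is already derived, so no new data are needed and trial conduct does not change. The drawback is that some incidental out-of-range values will be displayed.

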Missing	Known or ongoing	If medication stop date < date of first dose of IMP, assign as prior; If medication stop date ≥ date of first dose of IMP, assign as concomitant.
	Partial	If known components of medication stop date show that medication stopped before date of first dose of IMP, assign as prior; If known components of medication stop date show that medication stopped on or after date of first dose of IMP, assign as concomitant.
	Missing, not ongoing	Assign as concomitant.

A 2 CTCAE Toxicity Grade, Version 5.0

CTCAE Term	Laboratory test	Grade 1	Grade 2	Grade 3	Grade 4
Anemia	Hemoglobin (g/dL)	<LLN - 10.0	<10.0 - 8.0	<8.0	-
Eosinophilia ²	Absolute eosinophils	>ULN and >baseline	-	-	-
Leukocytosis	White blood cells (x 10E9/L)	-	-	>100	-
Cardiac troponin I increased	Troponin I (high sensitivity) ng/L	> 19.8 - <100 (males) >13.6 - <100 (females)	-	>= 100	-

CTCAE Term	Laboratory test	Grade 1	Grade 2	Grade 3	Grade 4
Activated partial thromboplastin (aPTT) time prolonged	aPTT (sec)	>ULN - 1.5 x ULN	>1.5 - 2.5 x ULN	>2.5 x ULN	-
Alanine aminotransferase (ALT) increased ¹	ALT (U/L)	>ULN - 3.0 x ULN if baseline was normal; 1.5 - 3.0 x baseline if baseline was abnormal	>3.0 - 5.0 x ULN if baseline was normal; >3.0 - 5.0 x baseline if baseline was abnormal	>5.0 - 20.0 x ULN if baseline was normal; >5.0 - 20.0 x baseline if baseline was abnormal	>20.0 x ULN if baseline was normal; >20.0 x baseline if baseline was abnormal
Alkaline phosphatase (ALP) increased ¹	ALP (U/L)	>ULN - 2.5 x ULN if baseline was normal; 2.0 - 2.5 x baseline if baseline was abnormal	>2.5 - 5.0 x ULN if baseline was normal; >2.5 - 5.0 x baseline if baseline was abnormal	>5.0 - 20.0 x ULN if baseline was normal; >5.0 - 20.0 x baseline if baseline was abnormal	>20.0 x ULN if baseline was normal; >20.0 x baseline if baseline was abnormal
Aspartate aminotransferase (AST) increased ¹	AST (U/L)	>ULN - 3.0 x ULN if baseline was normal; 1.5 - 3.0 x baseline if	>3.0 - 5.0 x ULN if baseline was normal; >3.0 - 5.0 x baseline if	>5.0 - 20.0 x ULN if baseline was normal; >5.0 - 20.0 x baseline if	>20.0 x ULN if baseline was normal; >20.0 x baseline if

CTCAE Term	Laboratory test	Grade 1	Grade 2	Grade 3	Grade 4
		baseline was abnormal	baseline was abnormal	baseline was abnormal	baseline was abnormal

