Hyponatremia	Sodium (mmol/L)	<LLN - 130	125-129	120-124	<120
Chronic kidney disease	Estimated glomerular filtration rate (eGFR) (ml/min/1.73m ²)	<LLN - 60	59 - 30	29 - 15	<15
Proteinuria	Urine protein	1+ proteinuria	Adult: 2+ and 3+ proteinuria	Adult: 4+ proteinuria	-

¹ Baseline grades, or post-baseline grades where no baseline visit available, follow the criteria defined for normal baseline results.

² Baseline grades, or post-baseline grades where no baseline visit available, do not follow criteria based on baseline results.

³ Derived only for participants not receiving anticoagulation medication.

⁴ Corrected serum calcium (mmol/L) derived $(0.02 * (40 \text{ g/L} - \text{albumin g/L})) + \text{serum calcium (mmol/L)}$.

Additional laboratory test may be collected if clinically indicated, at the discretion of the Investigator.

Source: https://ctep.cancer.gov/protocolDevelopment/electronic_applications/ctc.htm#ctc_50

A 3 Clinical Abnormalities: Vital Signs

Vital Signs Parameter	Vital Signs Grade			
	Mild (Grade 1)	Moderate (Grade 2)	Severe (Grade 3)	Potentially Life Threatening (Grade 4)
Fever (°C) (°F)	37.9-38.4	38.5-38.9	39.0-40	> 40
	100.1-101.1	101.2-102.0	102.1-104	> 104
Tachycardia (beats/minute)	101-115	116- 130	> 130	NA
Bradycardia (beats/minute) c	50-54	45-49	< 45	NA
Hypertension; systolic (mmHg)	141-150	151-155	> 155	NA
Hypertension; diastolic (mmHg)	91-95	96-100	> 100	NA
Hypotension; systolic (mmHg)	85-89	80-84	< 80	NA
Respiratory rate (breaths/minute)	17-20	21-25	> 25	NA

Hg = mercury. NA = not applicable.

Source: <https://www.fda.gov/media/73679/download>

A 4 Standardized MedDRA Query: Embolic and Thrombotic Events

It includes 3 sub standardized MedDRA queries:

- Embolic and thrombotic events, arterial (SMQ)
- Embolic and thrombotic events, venous (SMQ)
- Embolic and thrombotic events, vessel type unspecified and mixed arterial and venous (SMQ)

SIGNATURE PAGE

This is a representation of an electronic record that was signed electronically and this page is the manifestation of the electronic signature

Document Name: d8850c00010-sap-ed-2		
Document Title:	D8850C00010 Statistical Analysis Plan Edition 2	
Document ID:	Doc ID-004935358	
Version Label:	3.0 CURRENT LATEST APPROVED	
Server Date (dd-MMM-yyyy HH:mm 'UTC'Z)	Signed by	Meaning of Signature
24-Nov-2023 15:35 UTC	PPD [REDACTED] CYTEL	Author Approval
24-Nov-2023 15:13 UTC	PPD [REDACTED] (CLINCHOICE INC)	Content Approval
27-Nov-2023 08:21 UTC	PPD [REDACTED]	Author Approval

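### In the optional CTCAE laboratory shift table, an abnormal baseline liver test is graded against ULN but later values against the participant's own baseline, so unchanged and moderately rising values are tabulated as improvement.

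*SAP*

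**What the plan says.** Four parts of the SAP combine.

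- **Two grading scales (Appendix A 2).** For ALT and AST, Grade 1 is ">ULN - 3.0 x ULN if baseline was normal" but "1.5 - 3.0 x baseline if baseline was abnormal". Grade 2 on the relative scale is ">3.0 - 5.0 x baseline if baseline was abnormal". For ALP and GGT, the relative Grade 1 is "2.0 - 2.5 x baseline if baseline was abnormal". For bilirubin it is "> 1.0 - 1.5 x baseline if baseline was abnormal".
- **Which scale the baseline value gets (A 2, footnote 1).** "Baseline grades, or post-baseline grades where no baseline visit available, follow the criteria defined for normal baseline results". The baseline is thus always graded in multiples of ULN, even when it is abnormal.
- **What happens below the lowest cut (4.3.3.1).** For the shift summaries, "non-missing laboratory parameter results not meeting any of the 5 grades defined in the CTCAE toxicity grading system will be categorized as" No Event.
- **The table that uses the grades (4.3.3.2).** "Shift from baseline to the worst post-baseline observed value according to the CTCAE toxicity grades". It stands in a list of further summaries that may be provided, so it is optional.

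Nothing in the SAP reconciles the ULN-based baseline grade with the baseline-relative later grade.

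**The concern.** A shift table is read by comparing its row grade with its column grade, which requires one scale for both. Here, for a participant with an abnormal baseline, the row answers how far the value lies above ULN and the column answers how far it has moved from where it began. A cell below the diagonal then looks like improvement when the value has not moved, or has risen.

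Abnormal baselines are plausible in this trial. Protocol 5.1 admits people on active cancer treatment, transplant recipients and users of immunosuppressive drugs. Protocol 5.2 sets no liver-test limit. Protocol Appendix D 4.2 provides for participants who already met the potential Hy's Law criteria before starting IMP. At stake is a table of hepatic change that, if produced, points the wrong way for the participants in whom that change is hardest to judge.

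**Working it through.** The plan gives no figure of its own to reproduce here. The check applies the A 2 cuts as written.

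**Inputs (SAP Appendix A 2).** Upper ends of Grades 1, 2 and 3, in multiples of ULN (normal baseline) or of baseline (abnormal baseline):

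- ALT/AST: 3, 5, 20; lowest relative cut 1.5 x baseline
- ALP/GGT: 2.5, 5, 20; lowest relative cut 2.0 x baseline
- Bilirubin: 1.5, 3, 10; lowest relative cut just above 1.0 x baseline

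**Rule.** Baseline grade = ULN criteria applied to B, the baseline in multiples of ULN. If B > 1, the later grade = relative criteria applied to r = W / B, where W is the worst post-baseline value in multiples of ULN. No grade met = No Event.

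**Worked pairs.** The last column grades both time points on ULN.

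| Test | B to W (x ULN) | r | SAP table | ULN at both times |
|---|---|---|---|---|
| ALT | 4.0 to 4.0 | 1.0 | 2 to No Event | 2 to 2 |
| ALT | 4.0 to 5.9 | 5.9/4.0 = 1.475 | 2 to No Event | 2 to 3 |
| ALT | 4.0 to 7.0 | 7.0/4.0 = 1.75 | 2 to 1 | 2 to 3 |
| ALT | 4 to 12 | 3.0 | 2 to 1 | 2 to 3 |
| ALT | 6 to 30 | 5.0 | 3 to 2 | 3 to 4 |
| ALT | 4 to 12.4 | 3.1 | 2 to 2 | 2 to 3 |
| ALT | 4 to 20.4 | 5.1 | 2 to 3 | 2 to 4 |
| ALP | 3.0 to 5.9 | 5.9/3.0 = 1.97 | 2 to No Event | 2 to 3 |
| ALP/GGT | 2 to 3.8 | 1.9 | 1 to No Event | 1 to 2 |
| Bilirubin | 4.0 to 4.0 | 1.0 | 3 to No Event | 3 to 3 |
| Bilirubin | 4 to 12 | 3.0 | 3 to 2 | 3 to 4 |
| Bilirubin | 1.2 to 1.5 | 1.25 | 1 to 1 | 1 to 1 |

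**Ranges of r, from 1.0 upward, that read as improvement.** These follow by asking when the relative grade is lower than the baseline's ULN grade.

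| Test | Baseline Grade 1 | Baseline Grade 2 | Baseline Grade 3 |
|---|---|---|---|
| ALT/AST | below 1.5 | up to 3 | up to 5 |
| ALP/GGT | below 2.0 | up to 2.5 | up to 5 |
| Bilirubin | 1.0 only | up to 1.5 | up to 3 |

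At any baseline grade, an ALT/AST ratio below 1.5 or an ALP/GGT ratio below 2.0 goes all the way to No Event. Beyond the ranges shown, the rise appears as the same or worse.

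**Eosinophils.** Grade 1 requires a value above both ULN and baseline, and footnote 2 drops the baseline condition when the baseline itself is graded. A baseline above ULN is therefore Grade 1, while a later value still above ULN that does not exceed baseline is No Event. Creatinine, which shares footnote 2, escapes if its two listed criteria are alternatives, because a ULN criterion then still applies after baseline.

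**The case against.** The strongest reply is that this is one optional table among several and that the committed outputs do not depend on it. SAP 4.3.3.2 commits to observed values and change from baseline by visit, a table of maximum ALT/AST by maximum bilirubin in ULN bands, two heatmaps in multiples of ULN, a listing at ALT or AST of at least 3 x ULN or bilirubin of at least 2 x ULN, and a listing of out-of-range values. Every ALT and bilirubin value in the worked pairs at or above those thresholds would be listed; ALT at 5.9 or 7.0 x ULN falls in the band from 5 to below 10. The protocol adds central-laboratory alerts and SAE reporting of potential Hy's Law cases (Appendix D), and AE reporting of clinically relevant deterioration (8.3.6). The primary endpoint is AEs, SAEs and AESIs, with AE severity taken from the AE form, not from these grades.

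All of that stands, and it limits the consequence. A reader might infer that the plan would hide liver injury; for ALT, AST and bilirubin the documents do not support this. Two gaps remain. The ULN displays show post-baseline maxima, not movement from baseline. ALP and GGT have no display in multiples of ULN, and the normal-range shift table is reserved for parameters without CTCAE grades, so they have only by-visit summaries and the out-of-range listing.

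It can also be said that baseline-relative grades belong to the scale the SAP names and separate new change from pre-existing abnormality. That is a reason to keep them as a post-baseline count, not to cross them with a ULN-based baseline grade. A footnote explaining the two scales would warn the reader but leave the misdirected cells in place.

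**Conclusion.** The rule as written gives the wrong direction of shift for participants with an abnormal baseline whose worst value is unchanged or has risen within the ranges tabulated above. For ALT and AST these extend to a fivefold rise from a Grade 3 baseline. The same fault affects eosinophils that stay above ULN without exceeding baseline.

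Two broader statements might be inferred, and neither holds. The table is not directionless for everyone with an abnormal baseline: ALT from 2 to 6.2 x ULN, a ratio of 3.1, reads correctly as worse (Grade 1 to 2). Nor is every stable participant misplaced: the table takes the worst value over up to six post-baseline windows (SAP Table 6), and with a Grade 1 bilirubin baseline a small upward fluctuation restores Grade 1. That group is misplaced only when no later value exceeds baseline.

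Participants with normal baselines are unaffected. The number affected depends on the share with abnormal baseline tests, which the documents do not give; no figure is assumed here. The point matters only if the optional table is produced, and it does not touch the primary endpoint. The specification should still be corrected first, because a table produced to it would mislead.

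**What to change.** Amend SAP 4.3.3.2 and Appendix A 2 so that, if the CTCAE shift table is produced, both the baseline and the worst post-baseline value of ALT, AST, ALP, GGT and total bilirubin are graded on the normal-baseline (ULN) criteria whatever the baseline was, and eosinophils on exceeding ULN alone. If baseline-relative CTCAE grades are wanted, report them as a separate count of post-baseline grades, not crossed with a baseline grade.

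On a single scale the grade cannot fall unless the value falls, so no unchanged or rising value can appear as improvement; the last column of the worked pairs shows the result. The cost is brief SAP wording and a small programming change, with no new data and no change to the committed displays.
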